## Research Strategy

### Recruitment and Retention.

Clinicians working on the rehabilitation units will inform TBI patients of the study. If the patient is interested, the site-PI will discuss the study and obtain informed consent, which will include their permission for

the caregiver to participate. The site-PI will then invite the caregiver to participate and obtain informed consent. We selected a 12-month enrollment period because, based on TBI admissions data and previous studies conducted at the 3 sites, this window is necessary to enroll 110 dyads. Dyads will be randomly assigned to the treatment or control group, and each patient and caregiver will be paid the local currency equivalent of \$10 per data collection. Demographic and baseline data will be collected prior to discharge, as well as outcome data at 2 and 4 months post-discharge (Figure 2). A 4-month follow-up period was selected instead of a longer follow up because our research has suggested that the inpatient stay on an acute unit and the first 3 months post-discharge are the most stressful time periods for family TBI caregivers, and that their mental health and health related quality of life only increase marginally between 3 months and 1 year post-discharge. Therefore, the first several months after discharge are a critical time frame for intervention and follow up, as these variables remain fairly constant after initiating a particular trajectory.

**TBI Patient Inclusion Criteria.** All patients treated for TBI and discharged home will be invited to participate if they meet the following criteria: (1) give permission for their caregiver to participate; (2) sign an informed consent giving permission to obtain demographic and health information; (3) have the ability to communicate over the phone for data collection; and (4) are between 18-60 years of age. If a patient is aphasic (estimated 10%), arrangements will be made to collect data with self-administered paper-pencil reports via postal mail.

**Caregiver Inclusion Criteria.** TBI caregivers are eligible to participate who meet the following criteria: (1) have a telephone in the home or cellular phone and are able to talk on the phone; (2) sign an informed consent; (3) score at least a 13 on a health literacy screening tool; and (4) are between 18-85 years of age. Caregivers with scores below 13 will identify a family member or friend to review the guidebook with the caregiver. If no one is identified, the TAP clinician will review the materials with the caregiver.

**Sample Estimation and Power.** We anticipate that during a 12-month enrollment period, we will enroll approximately 110 caregiver-patient dyads ( $n = 220$ ), of which 55 will be in the treatment group and 55 will be in the control group. Of the 110 dyads, 20 will be in Cali, Colombia; 20 in Neiva, Colombia; and 70 in Mexico City, Mexico. Allowing for a 25% attrition rate based on our previous data collection with the TAP, over the 4-month data collection period, we estimate complete data on 84 dyads.

In order to determine the effect size that a final  $n$  of 84 dyads would be able to uncover, we performed a power analysis using G\*Power 3 software for a repeated measures multivariate analysis of variance (RMANOVA) with three time points and two groups. This RMANOVA would uncover all large and medium-size effects, as well as many small-size effects. Our prior pilot study on the TAP generally showed medium-size effects on caregiver strain and depression, so our estimated sample size should be sufficient. Additionally, in the proposed study, the intervention will include in-home interventions of 60-minute duration, as opposed to the 30-minute duration in our previous pilot study. We are therefore expecting a larger effect size in the proposed study. If the TAP is found to be effective based on these analyses, at the end of the study, caregivers in the control group will receive the caregiving guidebook that had been provided to the intervention group as well as a written summary of the problem solving techniques and skills addressed in the intervention.

**Transition Assistance Program Intervention.** [name], [name], and the site-PI will train a clinical psychologist at each rehabilitation facility to provide the TAP. Only clinical psychologists will serve as clinicians in order to reduce possible confounds from differing professional specialties of clinicians. The TAP involves three components to improve caregiver mental health and informal care: (1) skill development, (2) education, and (3) supportive problem solving. The TAP includes one face-to-face meeting between the clinician and caregiver prior to discharge, as well as an in-home visit to the caregiver in weeks 1, 2, 4, and 6.

**Guidebook Development.** Our research team will develop a guidebook entitled "A Guidebook for TBI Caregivers" based heavily on our research examining the needs of TBI caregivers in Latin America, as well as on other published studies on TBI. Our research has shown, for example, that the top reported needs of TBI NCT00207803

caregivers in this region include “To have a professional to turn to for advice,” “To have my questions answered honestly,” “To have enough resources for the patient,” and “To have explanations from professionals given in terms I can understand.” This guidebook will be created to target these needs directly and therefore likely include chapters addressing (1) basic medical information about TBI, (2) common caregiver experiences, (3) TBI recovery issues such as disability, disruption in sense of self, social isolation, and depression, and (4) resources to assist TBI caregivers. An extensive formative evaluation of the guidebook will include focus groups with TBI clinicians at the rehabilitation facilities in Mexico and Colombia, as well as with TBI clinicians and researchers at Virginia Commonwealth University. The guidebook will be translated into Spanish and piloted with TBI clinicians and caregivers at the rehabilitation sites in Colombia and Mexico who will provide quantitative and qualitative feedback on the guidebook’s appropriateness for Latino TBI caregivers. After the feedback is incorporated into the guidebook, it will be ready for further evaluation in this study. In the TAP for stroke caregivers which we implemented in Puerto Rico and Texas, we developed and piloted the guidebook in the first 2 months of that study’s timeline. For the current proposal, we doubled the estimated time for this deliverable in order to account for possible challenges in piloting the guidebook at 3—instead of 2—sites.

*Session 1.* In preparation for Session 1 with the caregiver, the rehabilitation clinician delivering the TAP will meet with the facility’s rehabilitation team to identify the primary difficulties anticipated for the TBI patient after discharge. The clinician will take notes on the particular needs of the patient and bring these notes to Session 1 with the caregiver. Before discharge, the clinician will implement Session 1, a 1-hour meeting with each caregiver in the intervention group only. The primary focus of Session 1 is to orient the caregiver to the TAP and prepare the caregiver for discharge home. The clinician will provide the caregiver a guidebook and orientation to it, encouraging the caregiver to use it as a resource.

The clinician will also administer the health literacy screening tool, and with caregivers who score below a 13, the clinician will help identify a family member or friend to review the guidebook with the caregiver. The clinician will then ask what concerns the caregiver has about taking care of the TBI patient after discharge, taking notes on the caregiver’s responses. The clinician will also share with the caregiver the primary difficulties that the rehabilitation team had anticipated the TBI patient experiencing after discharge. The clinician will provide support and help the caregiver problem-solve caregiving related to these issues.

*Sessions 2-5.* The clinician will make four 1-hour in-home visits to the TBI caregiver at 1, 2, 4, and 6 weeks after hospital discharge. The TBI patient may or may not be present during these visits, depending on the needs and wishes of the caregiver. These visits will involve the same general format. The clinician will bring his or her notes from the previous sessions and from the rehabilitation team’s input. The clinician will review the content of these notes with the caregiver, checking in to see whether the problems are still present and to what extent. The clinician will engage in supportive problem-solving and will refer the caregiver to the guidebook sections relevant to the issues, walking the caregiver through those sections. Because of this format, the TAP is specifically designed for clinicians to tailor its use not only according to possible cross-site differences in what may be necessary for the intervention, but also for differences in caregiver care responsibilities and needs within a single site. The entire structure of the TAP is centered around the caregiver’s most pressing needs. The clinician will take notes on the continued problems and the strategies for resolving them.

*Data Collection 1.* After enrollment and immediately before discharge (as well as before Session 1 for the treatment group), demographic and baseline data will be collected from the TBI patient and caregiver. The site-PI will meet with the patient and caregiver separately. The site-PI will read items aloud from an assessment packet to the patient and caregiver, circling participants’ responses. The caregiver packet will include validated measures of caregivers’ health status, health care utilization/cost, burden, depression, sense of coherence, quality of informal care provided, and relationship satisfaction. The patient packet will include validated measures of patients’ functional and health status, health care utilization/cost, self-perceived burden, depression, quality of informal care received, and relationship satisfaction.

*Data Collection 2-3.* At 2 and 4 months after hospital discharge, the site-PI will collect follow-up data from the TBI patient and caregiver over the phone using the same validated measures and in the same format as during Data Collection 1. For the treatment group only in Data Collection 2, the site-PI will also collect qualitative information from the

*Outcome Measures.* The majority of outcome measures have previously been translated and validated among Spanish speakers. For the four that have not (Exemplary Care Scale, Relationship Assessment Survey, Self-Perceived Burden Scale, and Brief Health Literacy Screening Tool), we will use Chapman and Carter’s methodology to translate and back-translate the measures, whereby a bilingual and bicultural researcher will translate the original measure into Spanish, and a separate bilingual and bicultural researcher blinded to the NCT00207803

original measure will then back-translate it into English. Any discrepancies between the original English and back-translated English will be resolved mutually. We will pilot the four translated measures with rehabilitation teams at each site and amend the instruments to improve their face validity in the three local cultures while ensuring the standardization of each instrument across the three sites. We will then administer the instruments over the course of our study, and after collecting outcome data, we will run exploratory factor analyses to establish each measure's factor structure, as we have done and advocated for in our own research investigating measure psychometrics among individuals after acute TBI and across various global regions. Based on these analyses, we will remove items that do not accurately measure the constructs under scrutiny.

*Functional Independence Measure (FIM; patient functional status).* The FIM is the most widely used method of assessing function and assistance needs in individuals with a disability. The FIM has a total score and six subscales: self-care, sphincter control, transfer capability, locomotion, communication, and social cognition. The FIM consists of 18 items, and responses use a 7-point ordinal scale. The reliability of the FIM is well established: in a meta-analysis the median inter-rater reliability for the total FIM was 0.95 and the median test-retest and equivalence reliability values of 0.95 and .92 respectively.

*Exemplary Care Scale (ECS; patient and caregiver rating of quality of informal care).* The ECS is an 11-item self-report questionnaire that assesses the extent to which caregivers engage or do not engage in activities that help care recipients maintain dignity and respect. Response choices are on a Likert scale (1 = never; 2 = sometimes; 3 = often; 4 = always), and higher scores indicate higher exemplary care. Parallel caregiver and care recipient versions are available, with equivalent measurement properties. The ECS has been shown to be a valid measure of the quality of informal care for individuals with disabilities.

*Patient Health Questionnaire-9 (PHQ-9; patient and caregiver depression).* The PHQ-9 is the depression-specific module of the Patient Health Questionnaire. The 9-item instrument directs the respondent to indicate how often he/she has been bothered by each item using a response from 0 (not at all) to 3 (nearly every day). Total score range from 0 to 27, and higher scores represent high depression. The Spanish version used for this study is reliable and valid in assessing depression in Spanish speakers.

*Relationship Assessment Survey (RAS; patient and caregiver relationship satisfaction).* The RAS is a 7-item scale originally developed to assess quality of marital relationships but was later adapted to apply for multiple types of interpersonal relationships (RAS-G). Item responses are on a 5-point Likert scale (1 = not satisfied and 5 = very satisfied), and higher scores represent higher satisfaction.

*Self-Perceived Burden Scale (SPBS; patient self-perceived burden).* The SPBS assesses care recipients' feelings of dependence and guilt over responsibility for their caregiver's difficulties. The SPBS contains 10 items which respondents rate with a 5-point Likert scale (1 = none of the time and 5 = all of the time), with higher scores indicating higher self-perception of a being a burden.

*Sense of Coherence Scale (SOC; patient and caregiver sense of coherence).* The SOC is a 13-item self-report questionnaire that assesses a person's tendency to perceive life events as meaningful, understandable, and manageable. Item responses range from 1 (never) to 7 (very often), and higher scores reflect a stronger sense of coherence. The Spanish SOC has good internal reliability and validity.

*Zarit Burden Interview (ZBI; caregiver burden).* The ZBI is one of the most widely used scales measuring subjective caregiver burden. It is a 22-item, self-report questionnaire with items referring to the caregiver/patient relationship and evaluating the caregiver's health condition, psychological well-being, finances, and social life. Responses can range from 'never' to 'nearly always,' and higher scores indicate greater levels of caregiver distress. The Spanish version of the ZBI has good internal reliability.

*36-Item Short Form (SF-36; patient and caregiver health status).* The SF-36 is one of the most widely used instruments to assess self-reported Health-Related Quality of Life (HRQoL) in individuals with TBI. The items address eight dimensions of health: physical function, role-physical, bodily pain, general health, energy/vitality, social function, role-emotional, and mental health. Scores range from 0-100, with higher scores indicating better health. It has been translated Spanish, and has well-established reliability and validity in Spanish-speaking populations.

*Brief Health Literacy Screening Tool (BRIEF; caregiver health literacy).* The BRIEF is a 4-item measure of health literacy level. In its initial construction, a factor analysis indicated that the BRIEF measures one distinct construct: "health literacy" (Eigenvalue = 2.4) accounting for 60% of score variance. The BRIEF has good convergent validity with other longer measures of health literacy.

*Overall Study Timeline.* An activity and milestone timeline for the 2-year grant cycle appears in Table 1.

Table 1. Grant Cycle Timeline							
Activity	Before Start	1-4 Months	5-8 Months	9-12 Months	13-16 Months	17-20 Months	21-24 Months
IRB	█						
Guidebook Development		█					
Guidebook Piloting							
Clinician Hiring		█					
Training		█					
Enrollment			█	█	█	█	
Intervention			█	█	█	█	
Data Collection			█	█	█	█	
Data Analyses				█	█	█	
Reports					█	█	
Publications						█	

NCT00207803

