A Culturally Sensitive Intervention for TBI Caregivers in Latin America

PI: [name]

NCT #: 02207803

Virginia Commonwealth University Internal Review Board (IRB): HM20001660

Document approval date: 5/6/2014

Document Type: SAP

What is the TAP's impact on Latino caregivers' health status, burden, depression, sense of coherence, quality of informal care provided, and relationship satisfaction?

Analytic Plan: A Greenhouse-Geisser-adjusted repeated measures multivariate analysis of variance (RMANOVA) with one fixed effect of treatment group (TAP vs. control), the repeated measures over time (baseline, and 2 and 4 months after discharge), and the treatment group by time interaction will be conducted for the set of dependent variables in Q1. If an omnibus effect is found, follow-up Bonferroni-corrected ANOVAs will identify specific locations of effects. These dependent variables rarely correlate with each other higher than .60,⁶¹ so do not reach the .70 level that Tabachnik and Fidell⁶² identify as problematic.

What is the TAP's impact on Latino TBI patients' functional and health status, self-perceived burden, depression, perceptions of quality of informal care received, and relationship satisfaction?

Analytic Plan: The same analyses will be used for the patient dependent variables.

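### No stratification by site is stated although two of the three sites have only 20 dyads each, and the SAP model has no site term: a low-cost loss of balance and precision

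*Protocol*

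**What the plan says.** On allocation, the Recruitment and Retention section of the protocol says "Dyads will be randomly assigned to the treatment or control group". It describes no list, blocking or stratification. It does not say that site is ignored either.

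The Sample Estimation and Power paragraph gives the site sizes, "Of the 110 dyads, 20 will be in Cali, Colombia; 20 in Neiva, Colombia; and 70 in Mexico City, Mexico", and the arm sizes, "of which 55 will be in the treatment group and 55 will be in the control group". It gives no split of arms within site. After dropout, "we estimate complete data on 84 dyads".

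The SAP specifies a repeated measures analysis "with one fixed effect of treatment group (TAP vs. control"), together with time (baseline, 2 and 4 months) and group by time. The patient outcomes get the same analysis. Here the absence of site is not a matter of silence: the SAP lists the terms of the model, and site is not among them.

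**The concern.** Site is a plausible predictor of outcome in this trial. The three sites lie in three cities and two countries. The site-PI collects all the data at each site, so interviewer and site coincide. Baseline is read aloud in person and follow-up is done by telephone, so an interviewer's influence could change between baseline and follow-up. The protocol itself expects the sites to differ in what the intervention will need.

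With 20 dyads at a site, an unstratified allocation can easily be uneven there. With no site term in the model, nothing in the analysis would correct for that, and variation between sites stays in the error term. What is at stake is the precision and credibility of the comparison in a trial of 84 expected completers, when both protections are almost free.

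**Working it through.** **Inputs from the documents.** 110 dyads, 20/20/70 by site, 55:55 by arm, 25% attrition, 84 completers, two groups, three time points.

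**Assumptions, because the documents give no site variance, SD, correlation or alpha.** Two-sided alpha 0.05; a standardised difference d = 0.5; 42 completers per arm; completers by site 15/15/54; correlation 0.5 between time points; site share s of the variance of the analysed contrast from 2% to 20%. Each outcome is treated singly, which simplifies the multivariate test.

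**1. The plan's own figure.** 110 × (1 − 0.25) = 82.5, against 84 stated (84/110 implies 23.6% loss). This is close enough, and 84 is used below.

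**2. Chance imbalance if allocation is not stratified, with 55:55 fixed overall.** The number of TAP dyads at a 20-dyad site is hypergeometric (110 dyads, 55 TAP, 20 drawn).

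| Split | A given small site | At least one of the two |
|---|---|---|
| 13:7 or worse | 0.22 | 0.38 |
| 14:6 or worse | 0.08 | 0.15 |

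One 14:6 split makes that site's share of the two arms differ by (14 − 6)/55 = 0.145. If the site differs from the others by 0.5 SD (assumed), the arm comparison moves by 0.145 × 0.5 = 0.073 SD. For the group-by-time test, the 0.5 SD would have to be a difference in change over time.

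**3. Which test is exposed.** Take a Colombia–Mexico difference D, total variance 1, and variance 0.5 between and 0.5 within persons. Among 84 completers the variance of the country indicator is 30 × 54/(84 × 83) = 0.232.

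- Group main effect (mean of three times): variance 0.5 + 0.5/3 = 0.667, SE = √(0.667 × 2/42) = 0.178. A stable D of 1 SD gives √((0.667 + 0.232) × 2/42) = 0.207.
- Group-by-time contrast (mean of the two follow-ups minus baseline): variance 0.5 × (1 + 1/2) = 0.75, SE = √(0.75 × 2/42) = 0.189. A stable D subtracts out; simulation gave 0.190 without it and 0.191 with D = 1.
- If instead the change over time differs by 1 SD between countries, the SE of that contrast becomes √((0.75 + 0.232) × 2/42) = 0.216.

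With D = 0.5 SD the site share is 0.058/(0.667 + 0.058) = 8% for the main effect, or 0.058/(0.75 + 0.058) = 7% for the interaction when the difference is in change. So 5% to 10% is what a moderate site difference would produce.

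**4. Size of the loss.** Leaving out site multiplies the variance by 1/(1 − s). Making that good takes 84/(1 − s) − 84 extra completers. Power is by the normal approximation for d = 0.5; with no site variance it is 0.63.

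| s | Variance factor | Completers | Power without site |
|---|---|---|---|
| 2% | 1.02 | 1.7 | 0.62 |
| 5% | 1.053 | 4.4 | 0.61 |
| 10% | 1.111 | 9.3 | 0.585 |
| 20% | 1.25 | 21 | 0.54 |

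**5. Type I error and the combinations** (simulation, site share 20%).

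| Allocation | Site in model | Type I error | Power |
|---|---|---|---|
| Unstratified | no | 0.047 | 0.53 |
| Unstratified | yes | 0.046 | 0.60 |
| Stratified | no | 0.030 | 0.52 |
| Stratified | yes | 0.051 | 0.61 |

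In the stratified, no-site row the model's SE averages 0.244 while the true SE is 0.219, so the test is too cautious.

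**6. Cost of the site term when site does not matter.** With balanced arms and two fewer error degrees of freedom (80 instead of 82), power by the noncentral t goes from 0.6196 to 0.6194.

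**The case against.** The strongest reply has four parts.

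*Allocation.* A reader might infer that randomisation ignores site. The protocol does not say that. Splits of 10:10, 10:10 and 35:35 would give 55:55 exactly, so the text is compatible with site-level lists. This stands: the supportable statement is that no stratification is stated.

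*Mechanism.* A reader might infer that all site variance falls on the treatment comparison. It does not. Baseline is one of the repeated measures, and a stable site difference cancels in group by time, the test that most directly shows a treatment effect here. This also stands. Two things remain. The SAP does not say which omnibus effect triggers the follow-up ANOVAs, so the group main effect is still in play. Site differences in change over time do reach the interaction.

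*Harm.* A reader might infer bias or false positives. Neither follows. Imbalance from randomisation averages to zero, and the simulated type I error of the unstratified model without site was 0.047 to 0.050. Nor is the trial shown to be short of power for the interaction: for a medium effect (f = 0.25) with 84 dyads, power is 0.97 or more, against 0.72 to 0.87 for the between-group effect, with correlations from 0.3 to 0.7.

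*Clinician.* One psychologist is trained per facility, but only TAP dyads see that person. Differences between psychologists are therefore differences in treatment effect by site. Neither stratification nor the site terms proposed here remove them, so the point does not rest on them.

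**Conclusion.** The point holds as a low-cost improvement in balance and precision, not as a flaw that invalidates the analysis. The SAP model omits site, and the protocol states no stratification. Without stratification there is about a 15% chance that a small site splits 14:6 or worse, and a loss equivalent to about 4 to 9 of 84 completers at an assumed site share of 5% to 10%. The loss is smaller if site matters less. For the group-by-time test it applies only to site differences in change over time.

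The modelling half of the point does not depend on how allocation is actually done. If allocation is unstratified, site terms recover most of the lost precision. If it is stratified, omitting site makes the test conservative whenever site matters. The sizes rest on assumed site variances, d = 0.5 and alpha 0.05, none of which the documents give.

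**What to change.** In the protocol, state the method, for example: dyads are randomised 1:1 within each site, using permuted blocks of varying size, from separate lists for the three sites. If this is already the practice, it only needs to be written down.

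In the SAP, add site (three levels) and site by time to both the caregiver and the patient models, including the follow-up ANOVAs. Site alone is not enough: a between-person site effect leaves the within-person group-by-time test unchanged, so site by time is the term that protects it. The two changes belong together, since stratifying without modelling site gives the conservative test shown above.

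The cost is three lists and a few degrees of freedom. Site takes 2 of the 82 between-person error degrees of freedom. Site by time takes 4 of the 164 within-person ones (82 × 2 = 164 becomes 80 × 2 = 160, before the Greenhouse-Geisser adjustment). No dyads, staff or visits are added.

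### A treatment-only task at month 2 for the person who collects the outcomes rules out a masked interviewer for the month-4 outcomes; deferring it is cheap

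*Protocol*

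**What the plan says.** Under Data Collection 1 in the Protocol, "The site-PI will read items aloud from an assessment packet to the patient and caregiver", and circles the responses. For the follow-up contacts (Data Collection 2-3), the Protocol states: "At 2 and 4 months after hospital discharge, the site-PI will collect follow-up data from the TBI patient and caregiver over the phone". The instruments and the manner of administration are those of the baseline contact. The next sentence begins "For the treatment group only in Data Collection 2, the site-PI will also collect qualitative information from the" and is then cut off in the extracted text. Who answers these questions, what they cover and where they fall within the call are therefore unknown. That they are put to one arm only is not in doubt.

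Three other places bear on the point:

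- **Training.** Under Transition Assistance Program Intervention, the site-PI is among those who "train a clinical psychologist at each rehabilitation facility to provide the TAP". That psychologist delivers the sessions, the last of them at week 6.
- **Exception to interviewing.** Under TBI Patient Inclusion Criteria, for aphasic patients (estimated at 10%), "arrangements will be made to collect data with self-administered paper-pencil reports via postal mail".
- **Allocation.** Under Recruitment and Retention, "Dyads will be randomly assigned to the treatment or control group". Neither document says who generates, holds or sees the assignment, and neither mentions masking or an independent assessor.

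**The concern.** One person asks the outcome questions and is also given a task that requires knowing the arm, two months before the last outcomes are collected. Controls are identified too, because they are the ones not asked.

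Most of the scales are self-reports read out by the interviewer: depression, caregiver burden, self-perceived burden, quality of care, relationship satisfaction, sense of coherence and health status. Tone, prompting and the coding of an unclear reply can move such answers. The interviewer also helped to train the clinician who delivers the programme, and so is not a neutral party. A shift that depends on arm and appears only after baseline would enter the group-by-time contrast on which the SAP relies. Nothing in the analysis could separate it from a true effect.

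**Working it through.** **Step 1: what the site-PI must know, and when.**

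| Contact | Who collects outcomes | Does the plan require knowledge of arm? |
|---|---|---|
| Baseline, before Session 1 | site-PI | No |
| Month 2 | site-PI, by phone | Yes, to put the treatment-only questions |
| Month 4 | site-PI, by phone | Already known from month 2 |

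For month 4 there is no way round this: all 84 dyads expected to complete would be interviewed by someone the plan has required to know the arm. For month 2 it depends on order. If the extra questions came after the outcome items of both patient and caregiver, and the arm were disclosed only then, month 2 could be protected. The Protocol does not set that order.

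**Step 2: how much of the data is collected this way.** The postal exception covers about 0.10 × 110 = 11 patients, or 11/220 = 5% of participants. The rest are interviewed by the site-PI.

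**Step 3: sample size for an illustration.** The Protocol (Sample Estimation and Power) gives 110 dyads, 25% attrition and 84 with complete data. 110 × 0.75 = 82.5, close to the stated 84 (84/110 implies 23.6% attrition). I use 84/2 = 42 per arm; 41 per arm changes little (7.3%, 14.6% and 26.9% in the first row below).

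**Step 4: effect of an assumed shift.** The documents give no shift, alpha or within-person correlation. I assume no true effect, a shift of *b* SD between arms after baseline, and two-sided 0.05.

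- *Raw month-4 comparison:* noncentral t on 82 df, noncentrality *b*/√(2/42), which is 0.458, 0.917 and 1.375 for *b* = 0.1, 0.2 and 0.3.
- *Group-by-time test for one outcome, three times, compound symmetry:* noncentral F on 2 and 164 df, noncentrality 21 × (2/3)*b*²/(1 − ρ). At ρ = 0.5 this is 0.28, 1.12 and 2.52. It is the same whether the shift is present at month 4 only or at both follow-ups.

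| False-positive rate | no shift | 0.1 SD | 0.2 SD | 0.3 SD |
|---|---|---|---|---|
| Raw month-4, 0.05 | 5% | 7.4% | 14.8% | 27.4% |
| Group-by-time, 0.05, ρ = 0.3 to 0.7 | 5% | 6.5–8.6% | 11.4–21.0% | 20.3–42.7% |
| Raw month-4, 0.05/6 = 0.0083 | 0.8% | 1.5% | 4.1% | 9.8% |

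The last row takes Bonferroni over the six caregiver constructs named in the SAP. That count is my assumption, since the SAP does not state the divisor.

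**The case against.** The strongest reply is that there is no blind to lose. The documents never say that the interviewer is masked. The site-PI obtains consent, collects baseline data and helps to train the clinician, and so may know the assignment from the start. On that view, moving one set of questions achieves nothing.

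Part of this stands. A reader might infer that the plan breaks a masking commitment, or that the treatment-only questions are the sole way in which the site-PI learns the arm. The documents support neither: they make no commitment, and they are silent on who sees the allocation. Training a psychologist in a programme does not show which dyads were assigned to it, but silence does not show that the site-PI is masked either. Deferring the questions is therefore of use only if the assignment is also withheld.

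A reader might also infer that every outcome is a subjective rating read aloud. That is too wide. Aphasic patients answer on paper, and both packets include health care utilization and cost, which is not plainly a subjective rating.

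Finally, the illustrated rates are not error rates for this plan. The SAP specifies an omnibus multivariate test followed by Bonferroni-corrected ANOVAs. The shift is assumed, and some of it could arise anyway if participants disclose their arm. What survives is the procedural point: as written, the month-2 task excludes a masked interviewer at month 4, and nothing elsewhere in the documents repairs this.

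**Conclusion.** The point holds in a limited form. As the data collection is written, a masked interviewer is impossible for the month-4 outcomes, and for month 2 as well unless the extra questions come after both members' outcome items. This follows from the text and needs no assumption.

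The size of any bias cannot be derived from the documents. On the assumptions above, a shift of 0.2 SD would roughly triple a nominal 5% error for a single raw month-4 comparison, to about 15%. At the stricter assumed Bonferroni level it would raise 0.8% to about 4%. These figures show that a modest shift matters at this sample size; they do not predict what would happen in this trial.

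This is a cheap improvement worth making. It is not evidence that the results would be invalid.

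**What to change.** 1. Remove the treatment-only questions from Data Collection 2. Ask them only after the month-4 outcome packets of both dyad members are completed and closed.
2. State who holds the allocation. Send each assignment to the TAP psychologist and withhold it from the site-PI until that dyad's month-4 packets are closed. Open each follow-up call by asking the participant not to mention any visits or the guidebook.
3. Have the site-PI record a guess of the arm after the packets are closed and before the arm is revealed for the qualitative questions. In any other order the guess tells nothing about masking.

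Putting the same neutral questions to both arms at month 2 would keep the timing. However, the answers could themselves reveal the arm before month 4, so deferral is the safer choice.

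**Cost.** The change is one of Protocol wording and of who receives the assignment. It needs no new assessor, although someone other than the site-PI must hold and release the allocation. Sessions end at week 6, so feedback would be given at month 4 instead of month 2, with poorer recall. Masking will remain imperfect because participants know their arm and may disclose it, and bias in their own self-reports is untouched.
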